7.1.1.1 Select Adverse Events (EU/ROW Submissions)

The select Adverse Events (select AEs) consist of a list of preferred terms grouped by specific category (e.g. pulmonary events, gastrointestinal events categories, etc.). AEs that may differ from or be more severe than AEs caused by non-immunotherapies and AEs whose early recognition and management may mitigate severe toxicity are included as select AEs. Categories of select AEs may include subcategories (e.g. adrenal disorders, diabetes, pituitary disorders, and thyroid disorders are subcategories of the endocrine event category).

The list of MedDRA preferred terms used to identify select adverse events is revisited quarterly and updated accordingly. The preferred terms used for the selection at the time of the database lock will be provided by categories/subcategories.

In addition to the frequency and worst severity of select AEs, time-to onset, time-to resolution, and time-to resolution where immune modulating medication was initiated will be analyzed for each specific category/subcategory of drug-related select AEs when applicable.

Further details on the definitions time-to onset and time-to resolution are described in [APPENDIX 1](#).

7.1.1.2 Other Events of Special Interest

Other events of special interest (OEOSI) consist of a list of preferred terms grouped by specific category (e.g. Myositis Event, Myocarditis Event, Demyelination Event, Guillain-Barre Syndrome, Pancreatitis Event, Uveitis Event, Encephalitis Event, Myasthenic Syndrome, Rhabdomyolysis Event, Graft Versus Host Disease). The list of MedDRA preferred terms used to identify OEOSI is revisited quarterly and updated accordingly. The preferred terms used for the selection at the time of the database lock by categories will be provided.

7.1.1.3 Immune-Mediated Adverse Events (US Submission)

In order to further characterize AEs of special clinical interest, analysis of immune-mediated AEs (IMAE) will be conducted. IMAEs are specific events (or groups of PTs describing specific events) that include pneumonitis, diarrhea/colitis, hepatitis, nephritis/renal dysfunction, rash, endocrine (adrenal insufficiency, hypothyroidism/thyroiditis, hypothyroidism, thyroiditis, hyperthyroidism, diabetes mellitus, and hypophysitis), and other specific events, considered as potential immune-mediated events by investigator that meet the definition summarized below:

- those occurring within 100 days of the last dose,
- regardless of causality,
- treated with immune-modulating medication (of note, endocrine AEs such as adrenal insufficiency, hypothyroidism/thyroiditis, hypothyroidism, thyroiditis, hyperthyroidism, diabetes mellitus, and hypophysitis are considered IMAEs regardless of immune-modulating medication use, since endocrine drug reactions are often managed without immune-modulating medication).
- with no clear alternate etiology based on investigator assessment, or with an immune-mediated component

The list of MedDRA preferred terms used to identify IMAEs is revisited quarterly and updated accordingly. The preferred terms used for the selection at the time of the database lock by categories will be provided.

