Cabozantinib and nivolumab both share category 1 NCCN guideline recommendations (ie, uniform consensus that the treatment is appropriate, based on high-level evidence) for the treatment of previously treated mRCC patients.⁶ Therefore, it is an appropriate next step to combine these agents and move them to the first-line setting in an attempt to improve clinical outcomes in patients with advanced RCC. This protocol CA2099ER will test the clinical activity of nivolumab combined with cabozantinib (doublet regimen). Given the different mechanisms of action of each of these agents, there is potential for distinct improvement in clinical efficacy.⁷

[REDACTED]

[REDACTED]

[REDACTED]

[REDACTED]

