9.2 Adverse Events

The definitions of an AE or serious adverse event (SAE) can be found in [Appendix 3](#).

AEs will be reported by the participant (or, when appropriate, by a caregiver, surrogate, or the participant's legally authorized representative).

The investigator and any designees are responsible for detecting, documenting, and reporting events that meet the definition of an AE or SAE and remain responsible for following up AEs that are serious, considered related to the study treatment or the study, or that caused the participant to discontinue before completing the study.

Contacts for SAE reporting specified in Appendix 3

Immune-mediated adverse events (IMAEs, imAEs) are AEs consistent with an immune-mediated mechanism or immune-mediated component for which non-inflammatory etiologies (eg, infection or tumor progression) have been ruled out. IMAEs can include events with an alternate etiology which were exacerbated by the induction of autoimmunity. Information supporting the assessment will be collected on the participant's case report form.

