6 STUDY PERIODS, TREATMENT REGIMENS AND POPULATIONS FOR ANALYSES

6.1 Study Periods

- Baseline period:
 - Baseline evaluations or events will be defined as evaluations or events that occur before the date and time of the first dose of study treatment. Evaluations (laboratory tests, pulse oximetry and vital signs) on the same date and time of the first dose of study treatment will be considered as baseline evaluations. Events (AEs) on the same date and time of the first dose of study treatment will not be considered as pre-treatment events.
 - In cases where the time (onset time of event or evaluation time and dosing time) is missing or not collected, the following definitions will apply:
 - ◆ Pre-treatment AEs will be defined as AEs with an onset date prior to but not including the day of the first dose of study treatment;
 - ◆ Baseline evaluations (laboratory tests, pulse oximetry and vital signs) will be defined as evaluations with a date on or prior to the day of first dose of study treatment.
 - If there are multiple valid assessments on or prior to the first dose of study treatment:
 - ◆ For laboratory tests, the latest non missing labs value on or before first dose date (and time if collected) will be used as the baseline in the analyses. For 'LIPASE' and 'GLUCOSE', for treated subjects only, the last predose assessment with non-missing toxicity grade will be considered as baseline. If multiple assessments exist with the same collection date (and time if collected) and entry date and time, then the first observation is used as baseline.

- Post baseline period:
 - On-treatment AEs will be defined as AEs with an onset date and time on or after the date and time of the first dose of study treatment (or with an onset date on or after the day of first dose of study treatment if time is not collected or is missing). For subjects who are off study treatment, AEs will be included if event occurred within a safety window of 30 days (or 100 days depending on the analysis) after the last dose of study treatment. No “subtracting rule” will be applied when an AE occurs both pre-treatment and post-treatment with the same preferred term and grade.

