7.6.7 Immune-Mediated Adverse Events (US Submission)

IMAEs will be summarized by treatment group for each immune-mediated category / PT using the 100-day safety window:

- Overall summary of non-endocrine IMAEs by worst CTC grade (any grade, grade 3-4, grade 5) where immune modulating medication was initiated presented by Category / PT.
- Overall summary of endocrine IMAEs by worst CTC grade (any grade, grade 3-4, grade 5) presented by Category / PT.
- Overall summary of non-endocrine IMAEs leading to discontinuation by worst CTC grade (any grade, grade 3-4, grade 5) where immune modulating medication was initiated presented by Category / PT.
- Overall summary of endocrine IMAEs leading to discontinuation by worst CTC grade (any grade, grade 3-4, grade 5) presented by Category / PT.
- Overall summary of non-endocrine IMAEs leading to dose delay or reduction by worst CTC grade (any grade, grade 3-4, grade 5) where immune modulating medication was initiated presented by Category / PT
- Overall summary of endocrine IMAEs leading to dose delay or reduction by worst CTC grade (any grade, grade 3-4, grade 5) presented by Category / PT.
- Summaries of time-to onset and time-to resolution of non-endocrine IMAEs where immune modulating medication was initiated presented by Category.
- Summaries of time-to onset and time-to resolution of endocrine IMAEs presented by Category.

A by-subject listing of IMAEs will be provided. By-subject listings of time-to resolution for longest IMAEs cluster (any grade and grade 3-5 in separate summaries) will also be provided. For new studies which collect investigator assessment of potential IMAE data, a by-subject listing of AEs considered as immune-mediated events per investigator but not qualified for IMAEs definition will also be provided.

In addition, for all nivolumab treated subjects who experienced at least one IMAE, the following data presentation will be provided:

- Summary of subjects who were re-challenged with nivolumab by IMAE category, with extended follow-up
- Summary of subjects who were re-challenged with nivolumab or ipilimumab by IMAE category, with extended follow-up

For these, re-challenge is considered to have occurred when last nivolumab and/or ipilimumab infusion was administered after the onset of an IMAE.

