7.6.8 Other Events of Special Interest

OEOSI will be summarized by treatment group for each category.

The following analyses will be conducted using the 100-day safety window:

- Overall summary of OEOSI by worst CTC grade (any grade, grade 3-4, grade 5) presented by Category / PT
- Overall summary of drug-related OEOSI by worst CTC grade (any grade, grade 3-4, grade 5) presented by Category / PT

A by-subject listing of OEOSI will be provided.

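### The 100-day immune-mediated and all-causality special-interest event tables neither stop at nor flag subsequent therapy, so immune toxicity from a later checkpoint inhibitor can be counted in the sunitinib arm

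*SAP*

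**What the plan says.** **IMAE definition (SAP 7.1.1.3).** Qualifying events are "those occurring within 100 days of the last dose" and are counted "regardless of causality". Non-endocrine events must have been treated with immune-modulating medication; endocrine events need not have been. The investigator must regard the event as potentially immune-mediated, and it must be "with no clear alternate etiology based on investigator assessment, or with an immune-mediated component".

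**IMAE tables (SAP 7.6.7).** "IMAEs will be summarized by treatment group for each immune-mediated category / PT using the 100-day safety window". No version restricted to drug-related events is listed.

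**OEOSI tables (SAP 7.6.8).** "The following analyses will be conducted using the 100-day safety window". Two tables follow: the first has no causality restriction and the second is limited to drug-related events.

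**Closing the window (SAP 6.1).** For participants off study treatment, "AEs will be included if event occurred within a safety window of 30 days (or 100 days depending on the analysis"), counted from the last dose. Subsequent therapy is not mentioned.

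**Arm assignment (SAP 6.2).** The as-treated group equals the randomized group unless the wrong drug was given for the whole treatment period. A later switch does not move a participant.

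**Protocol 9.2.** IMAEs are events "for which non-inflammatory etiologies (eg, infection or tumor progression) have been ruled out". Some events with another cause may still qualify if induced autoimmunity made them worse.

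**The concern.** The efficacy definitions deal explicitly with subsequent therapy: primary PFS (SAP 4.1.1), best overall response (4.2.2) and duration of response (4.2.2.2) all stop or censor at it. The 100-day safety tables have no counterpart.

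This matters because a switch is foreseeable. Protocol 8.1 makes progression a reason to stop study treatment. Protocol 3 says of previously treated disease: "Cabozantinib and nivolumab both share category 1 NCCN guideline recommendations". Prior PD-1 or PD-L1 therapy was an exclusion, so Arm C participants enter follow-up without such exposure, whereas Arm A participants have already had nivolumab. Adverse events are collected for at least 100 days after last dose, with an in-person visit at about day 100, so immune events on a second-line drug would be captured.

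At stake is the comparison of immune toxicity between doublet and sunitinib in tables labelled for US submission (the IMAE set) and in the all-causality OEOSI table. Events added to the control arm make the doublet look less immunotoxic than it is. A reader of the tables could not see this, because nothing separates events before a switch from events after it.

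**Working it through.** **Step 1. Trace one case through the rules.** Take a treated Arm C participant who stops sunitinib at progression, starts a PD-1 antibody some weeks later, and develops colitis treated with steroids, all within 100 days of the last sunitinib dose.

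| Rule | Source | Result |
|---|---|---|
| Within 100 days of last study dose | SAP 7.1.1.3, 6.1 | Met |
| Causal link to study drug | SAP 7.1.1.3 | Not required |
| Immune-modulating medication | SAP 7.1.1.3 | Met (not needed for an endocrine event) |
| Potentially immune-mediated per investigator | SAP 7.1.1.3 | Expected to be met |
| No clear alternate etiology | SAP 7.1.1.3 | May fail if the investigator names the new drug |
| Or an immune-mediated component | SAP 7.1.1.3 | Can be met by the nature of the event |
| Arm | SAP 6.2 | Arm C |
| Removed or flagged because of subsequent therapy | No readable safety text | No |

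The etiology condition is joined by *or*, so failing its first branch does not exclude the event. For an OEOSI term, the first table in SAP 7.6.8 counts the event under the default in SAP 7.1.1 (on-treatment events whatever the cause). The second counts it only if the CRF relationship to study drug is Related or missing.

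**Step 2. Effect on the contrast.** Let *s* be the share of an arm starting a checkpoint inhibitor inside the window, and *r* the chance of a first qualifying event in the rest of it. The difference (Arm A minus Arm C) is then understated by

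s_C × r_C − s_A × r_A.

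Equal products in the two arms give no bias in the difference; only the excess in Arm C matters.

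**Step 3. Illustrative size.** The documents give no figure for *s* or *r*, so there is nothing to reproduce. Both are assumed here. The denominator is the planned 319 per arm (randomized; the treated number may be smaller). With s_A × r_A set to zero, the least favourable case:

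| s_C | r_C | Participants added, 319 × s_C × r_C | Points added to Arm C rate |
|---|---|---|---|
| 10% | 5% | 1.6 | 0.5 |
| 25% | 10% | 8.0 | 2.5 |
| 40% | 20% | 25.5 | 8.0 |

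**Step 4. Are those switch rates compatible with the plan?** Assume exponential PFS with the planned medians (12.4 and 18.2 months) and follow-up spread evenly over 10 to 25 months at the 29-month analysis. The expected event fraction is

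1 − [exp(−10λ) − exp(−25λ)] / (15λ), with λ = ln 2 / median.

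- Arm C: λ = 0.0559; 1 − (0.572 − 0.247)/0.839 = 0.61, or about 196 of 319.
- Arm A: λ = 0.0381; 1 − (0.683 − 0.386)/0.571 = 0.48, or about 153 of 319.
- Total: about 349, in line with the plan's 350.

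Switch rates of 10%, 25% and 40% mean about 32, 80 and 128 starters, or 16%, 41% and 65% of the 196 Arm C PFS events. Those events include deaths and progressions just before the cut-off, so the top rate is demanding. It is not a strict bound, because participants who stop for toxicity can also switch.

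**The case against.** Several points on the other side stand.

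- **Causality is not ignored throughout.** A reader might infer that all the special-interest tables disregard it. They do not: SAP 7.6.8 plans a drug-related OEOSI table, and SAP 7.6.5 repeats the drug-related AE summary with the 100-day window. The gap concerns the IMAE tables and the first OEOSI table.
- **The etiology criterion can remove some events.** An investigator may name the new antibody as a clear alternate cause, and SAP 7.1.1.3 does not limit alternate causes to non-inflammatory ones; infection and progression in Protocol 9.2 are only examples. It would be too strong to say that every post-switch immune event will be charged to Arm C. The second branch of the criterion nevertheless leaves the filter unreliable.
- **The rule is symmetric.** Post-switch events in Arm A are counted too. Protocol 3 names cabozantinib beside nivolumab as an option in previously treated disease, so a sunitinib participant need not move to a checkpoint inhibitor. Protocol 8.1.4 lets either arm continue beyond progression, which delays switching. A reader might infer that bias against the control arm is established; the documents make it plausible but do not show it.
- **The consequences are limited.** Safety analyses are descriptive. SAEs, discontinuations, select AEs and most general AE tables use 30 days. By-subject IMAE and OEOSI listings are planned, so individual events might be traced.
- **Not everything is visible.** Parts of the SAP are redacted, and table mock-ups sit in a separate Data Presentation Plan, so a flag specified there cannot be ruled out.

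None of this supplies a rule, in the readable text, that separates events before and after a switch.

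**Conclusion.** The concern holds for the IMAE tables and the all-causality OEOSI table. As written, they can count in Arm C immune events caused by a checkpoint inhibitor started after sunitinib, and the planned tables give no means of seeing how many. Understatement of the doublet's excess immune toxicity requires more checkpoint-inhibitor starts within 100 days in Arm C than in Arm A, or a higher event risk after them. The direction is plausible and the size unknown. The range of 0.5 to 8.0 percentage points rests wholly on assumed rates and on no offsetting events in Arm A. No hypothesis test, alpha allocation or sample size is affected.

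A reader might also infer that the planned tables should be replaced by truncated ones. The documents do not support that. The contraception interval in Protocol 6.1 (5 months, made up of 30 days plus about five half-lives) implies roughly four months for five half-lives, longer than the 100-day window. True late nivolumab events after a switch are therefore possible, and truncation alone would drop them from Arm A and so also understate the doublet's toxicity.

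**What to change.** Keep the 100-day tables as planned. Add to SAP 7.6.7 and 7.6.8 a parallel between-arm display, applied identically to both arms, that excludes or separately flags events with onset on or after the start of the first subsequent systemic anti-cancer therapy.

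Derive that date from the subsequent-therapy data already collected (Protocol 5.1 has new anti-tumor therapy recorded on the CRF). The subsequent-therapy date used for PFS censoring should not simply be reused: SAP 4.1.1 also counts tumor-directed radiotherapy and surgery, so the first such date need not be systemic treatment.

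The cost is SAP wording, one derived date and one extra run of existing tables, with no change to treatment, visits or data collection. The downside is that the added display omits some true late nivolumab events, so it should be read beside the untruncated table and not in its place.

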7.1.2 Laboratory Tests

Clinical laboratory parameters (hematology, serum chemistry and electrolytes) will be evaluated.

Laboratory tests will be graded using the NCI Common Terminology Criteria, and the most recent version of the criteria at the time of the database lock will be used.

Clinical laboratory data will be first analyzed using International System of Units (SI).

Analyses will be repeated using US conventional units.

In the laboratory summary tables, unless otherwise specified, subjects will be counted only once for each lab parameter according to their worst on treatment CTC grade (worst being the highest

CTC grade). The laboratory tables and listings will be sorted by laboratory category, laboratory subcategory and laboratory test code sequence number.

7.2 Study Conduct

The following programmable deviations will be considered as relevant protocol deviations and summarized by treatment group and overall in all randomized subjects. Non-programmable relevant eligibility and on-treatment protocol deviations, as well as significant (both programmable and non-programmable) eligibility and on-treatment protocol deviations will be reported through ClinSIGHT listings.

Eligibility:

- Subjects with baseline KPS < 70%
- Subjects who received prior systemic anti-cancer treatment in the metastatic setting
- Subjects without histologically confirmed RCC with a clear-cell component, documented advanced or metastatic RCC

On-study:

- Subjects receiving anti-cancer therapy (chemotherapy, hormonal therapy, immunotherapy, standard or investigational agents for treatment of cancer) while on study therapy
- Subjects treated differently than as randomized (subjects who received the wrong treatment, excluding the never treated)

Enrollment by country and site, and enrollment by month will be summarized and listed for all enrolled subjects.

A by-subject listing of batch numbers for all treated subjects will be provided.

7.3 Study Population

Analyses in this section will be tabulated for all randomized subjects by treatment group as randomized, unless otherwise specified.

7.3.1 Subject Disposition

The total number of subjects enrolled (randomized or not randomized) will be presented along with the reason for not being randomized. This analysis will be performed on the all enrolled subjects population only.

Number of subjects randomized but not treated along with the reason for not being treated will be tabulated by treatment group as randomized.

Number of subjects who discontinued study treatment along with corresponding reason will be tabulated by treatment group as treated. Reason for discontinuation will be derived from subject status CRF page. This analysis will be performed only on the all treated subjects population.

A by-subject listing for all treated subjects will be provided showing the subject's off treatment date and whether the subject continue in the study along with the reason for going off study. A by-subject listing for all enrolled subjects will also be provided, showing whether the subject was randomized along with the reason for not being randomized.

Note that for all intermediate/poor risk treated subjects in Arm A and Arm C, number of subjects who discontinued study treatment along with corresponding reason will be tabulated by treatment group as treated.

7.3.2 Demographics and Other Baseline Disease Characteristics

The following demographic and baseline disease characteristics will be summarized and listed by treatment group as randomized:

- Age
- Age categorization (< 65, ≥ 65 and < 75, ≥ 75 and < 85, ≥ 85, ≥ 75, ≥ 65)
- Sex (Male, Female)
- Race
- Region (Region (US/Canada/W.Europe/N.Europe vs. ROW) (source: IRT)
- Ethnicity (Hispanic/Latino and Not Hispanic/Latino)
- Karnofsky performance status (70, 80, 90, 100)
- Baseline IMDC prognostic score (0, 1-2, ≥ 3) (source: IRT)
- Baseline IMDC prognostic score (0, 1-2, ≥ 3) (source: CRF)
- Time from initial disease diagnosis to randomization (<1 year, ≥1 year)
- Baseline LDH level (≤ 1.5 x ULN, >1.5 x ULN)
- Hemoglobin (<LLN, ≥ LLN)
- Corrected Calcium (≤ 10 mg/dl, >10mg/dl)
- Absolute Neutrophil Count (≤ ULN, > ULN)
- Platelet Count (≤ ULN, > ULN)
- Baseline Alkaline phosphatase (< ULN, ≥ ULN)
- Prior nephrectomy (Yes, No)
- Prior radiotherapy (Yes, No)
- Baseline PD-L1+ status based on a 1% cut off (≥ 1% vs. < 1% or indeterminate)
- Baseline PD-L1+ status based on a 5% cut off (≥ 5% vs. < 5% or indeterminate)
- Baseline PD-L1+ status based on a 10% cut off (≥ 10% vs. < 10% or indeterminate)

- Number of disease sites per subject (1, 2, 3, 4 , >4)
- Tumor burden: sum of the diameters of target lesions at baseline
- Most common sites of metastasis
- Sarcomatoid features (Yes, No)
- Stage at the initial diagnosis (Stage IV, non-Stage IV)
- Pre-treatment events tumor assessment (per Investigator)

Summary table (cross-tabulation) by treatment group for stratification factor (except for region) will be provided to show any discrepancies between what was reported through IRT vs. CRF at baseline. This summary will be performed based on all randomized subjects.

- IMDC Prognostic Score: 0 versus 1-2 versus 3-6
- Region: US/Canada/W Europe/N Europe versus ROW
- PD-L1 tumor expression: $\geq 1\%$ versus $< 1\%$ or indeterminate

A listing of randomization scheme presenting randomized treatment group and as treated treatment group will be provided for all randomized subjects.

Note that for all intermediate/poor risk subjects in Arm A and Arm C, demographic and baseline disease characteristics will be summarized and listed by treatment group as randomized.

